11.0 ADVERSE EVENTS AND REPORTING

The timely reporting of adverse events (including toxic deaths) is required by the Food and Drug Administration. The reporting of toxicities is part of the data reporting for this study. The sponsor-investigator is responsible for ensuring that all adverse events (AEs) and serious adverse events (SAEs) that are observed or reported during the study are collected. Misuse and abuse of the study medication, medication errors and uses outside of what is foreseen in the protocol (irrespective if a clinical event has occurred) must be reported within 24 hours to the Study Sponsor/ Principal Investigator.

Adverse Events

Property of University of Pennsylvania
Confidential

The PATCH Trial

An **adverse event** (AE) is any symptom, sign, illness or experience that develops or worsens in severity during the course of the study that does not necessarily have a causal relationship with this treatment. Intercurrent illnesses or injuries should be regarded as adverse events. Abnormal results of diagnostic procedures are considered to be adverse events only if the abnormality:

- results in study withdrawal
- is associated with a serious adverse event
- is associated with clinical signs or symptoms
- leads to additional treatment or to further diagnostic tests is considered by the investigator to be of clinical significance

Adverse Event Reporting Period

The study period during which adverse events must be reported is defined as the period from the initiation of the first study treatment to the last administration of study treatment.

Post-study Adverse Event.

All unresolved adverse events should be followed by the clinical investigator until the events are resolved, the participant is lost to follow-up, or the adverse event is otherwise explained. At the last scheduled visit, the investigator should instruct each participant to report any subsequent event(s) that the participant, or the participant's personal physician, believes might reasonably be related to participation in this study.

Abnormal Laboratory Values.

A clinical laboratory abnormality should be documented as an adverse event if the abnormality is grade 1 or more and a change from baseline.

11.1 Recording of Adverse Events.

At each contact with the participant, the appropriately delegated and credentialed study team member must seek information on adverse events by specific questioning and, as appropriate, by examination. Information on all adverse events should be recorded immediately in the source document, and also in the appropriate adverse event module of the case report form (CRF). All clearly related signs, symptoms, and abnormal diagnostic procedures results should be recorded in the source document, though should be grouped under one diagnosis.

All adverse events occurring during the study period must be recorded. Adverse events will be measured and graded in accordance with the CTCAE. The clinical course of each event should be followed until resolution, stabilization, or until it has been determined that the study treatment or participation is not the cause. Serious adverse events that are still ongoing at the end of the study period must be followed up to determine the final outcome. Any serious adverse event that occurs after the study period and is considered to be at least possibly related to the study treatment or study participation should be recorded and reported immediately.

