Asymptomatic PCR+ at baseline: Given the 20% prevalence of asymptomatic coronavirus infection, we will need to screen 250 subjects to accrue the target enrollment of 200 to address the primary endpoint. If the PCR test returns positive while the health care worker is enrolled on the study, the participant will be notified and offered to be removed from the study or to continue with the study medication. Baseline PCR+ subjects who decide to withdraw from the study will be asked to go to occupational health and seek the care of their primary physician. Their study medication will remain blinded and the subject will be asked not to take any additional study medication. For baseline PCR+ subjects who decide to continue on study, they will be asked to keep the daily pill diary. If these subjects are asymptomatic after one week of study medication, they will be asked to return to undergo an on treatment nasopharyngeal swab. If the subject develops symptoms on study medication after 7 days of treatment, the subject will be unblinded. If the subject was assigned to placebo, they will have the option to crossover and get treatment with HCQ 600 mg qd for up to 7 days. Weekly phone calls per the sub-study 3 schedule will continue during this time. AEs will be reported as planned for the study. Baseline PCR+ subjects will be replaced in the prevention study related to the primary objective of sub-study 3 and will not count towards the target accrual or interim analysis. Baseline PCR negative subjects who screen positive at the one month or two-month mark will be considered COVID-19 positive as it relates to the primary endpoint.

Asymptomatic PCR+ at one month: These subjects will count towards the primary endpoint of sub-study 3 as an infection event. Accordingly, they will be unblinded and if on placebo they will be allowed to crossover to HCQ 600 mg qd for 2 weeks. If the subject is assigned to HCQ and turns PCR positive while asymptomatic, the subject will be stopped from study drug and referred to occupational health for standard of care management of health care worker infection. Weekly phone calls will continue. If the subject remains asymptomatic after one month, he/she will return for the one-month swab.

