9.0 SCHEDULE OF EVENTS

Table 4. Schedule of events for sub-study 1			
	Before treatment	During treatment	Day of release from quarantine
Eligibility checklist	X		
Temperature (patient obtained)		Twice daily	X
COVID-19 symptom score		Daily	
Mobile Cardiac Telemetry	X	Daily	X
AE assessment, triage		Daily as needed	X
SARS-COV-2 PCR nasopharyngeal swab	X		
SARS-COV-2 PCR nares swab ¹	X	D3, D7	X (if ≤7 or 10 days, per CDC guidelines)
Oral fluid collection ²	X	D3, 7	X
TREATMENT			
Hydroxychloroquine or placebo		Twice every day	Return electronic diary

1- The nares swab before treatment sample can be performed at any time of day and should be collected before any study medication has been taken.

The PATCH Trial

2-For oral fluid collections, these should be performed in the morning to maintain consistency. For the before treatment collection, if HCQ is received during the day, there should not be a delay in starting HCQ in order to collect morning oral fluid. Instead study medication should be started and the next morning the first sample can be collected and considered the baseline sample. The timing of collection should be recorded in the daily diary.

Table 6. Schedule of events for Sub-study 3			
	Baseline / Pre-RX	During 2 months	End of 2 months
Eligibility checklist	X		
COVID-19 symptom score	X	Weekly	
AE check by telephone		1X/week	X
PCR SARS-COV-2 ¹	X	One month	X ²
Oral fluid collection	X	Every 2 weeks	X
Research Blood ²	X	One month	X
6 or 12 Lead Electrocardiogram	X	One month	
TREATMENT			
Hydroxychloroquine or placebo		3 pills daily	

- 1- this testing is dependent on availability of the test kits and can be deferred if test kits or testing capacity are not available
- 2- End of 2 months or at the time of symptom progression 3- one 10-mL tiger top serum separator tubes (SST). This collection can be deferred to accommodate the conditions of the COVID-19 crisis situation and how it affects resources and health care worker schedules.
- 3- If subject has had an EKG in the last 6 months the baseline EKG can be deferred. Since this EKG is for research purposes only, the serial EKGs can be deferred to accommodate the conditions of the COVID-19 crisis and how it affects resources and health care worker schedules.

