10.0 MEASUREMENT OF EFFECT

10.1 Definitions

Evaluable for toxicity. All participants will be evaluable for toxicity from the time of their first treatment with HCQ or placebo.

Evaluable for primary outcome: Participants who received at least one dose of study drug will be evaluable for the primary outcome as long as they meet the following status for SARS-COV2 PCR: sub-study 1: PCR+ Sub-study 3: PCR negative.

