In addition, at our second interim analysis for SS3, we will evaluate the conditional power based on our original assumptions. The actual effect size for this study is completely unknown. If the effect size is smaller than we anticipated but still promising, and our conditional power falls between 0.5 and 0.8, we will consider formally adjusting the sample size in SS3 to achieve a conditional power of 0.8 based on an updated understanding of the effect size (29).

Z-Value Boundaries			
	Boundaries		Information
Stage	Efficacy	Futility	Proportion
1	2.9473	-1.2318	0.2500
2	2.5825	-0.2676	0.5000
3	1.6664	1.6664	1.0000

P-Value Boundaries			
	Boundaries		Information
Stage	Efficacy	Futility	Proportion
1	0.00160	0.89099	0.2500
2	0.00491	0.60550	0.5000
3	0.04782	0.04782	1.0000

12.2 Analysis of Secondary Endpoints.

Secondary outcomes will at least be analyzed as summary statistics, with group means, odds-ratios, and 95% CIs. We may conduct exploratory analyses using regression methods appropriate for each type of measure.

Sub-Study 1: Rate of secondary infection of housemates is a binomial count by household. We will summarize the proportion or rate by group, with 95% CI. With sufficient data, we will explore subgroups, patient, and secondary patient characteristics using logistic regression. Rate of hospitalization is a binary measure. We will summarize rates by group, and estimate the odds-ratio for treatment. Adverse event rates will be summarized as a count by subject, and mean count by group, and we will estimate a rate-ratio for treatment.

Sub-Study 3: For hospital employees, Adverse event rates will be summarized as a count by subject, and mean count by group, and we will estimate a rate-ratio for treatment.

REFERENCES

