The timely reporting of adverse events (including hospitalizations and deaths) is required by the Food and Drug Administration. The reporting of medication toxicities and other adverse events is part of the data reporting for this study. The sponsor-investigator is responsible for ensuring that all adverse events (AEs) and significant adverse events (SAEs) that are observed or reported during the study are collected.

Adverse Events

An adverse event (AE) is any symptom, sign, illness or experience that develops or worsens in severity during the course of the study that does not necessarily have a causal relationship with this treatment. Intercurrent illnesses or injuries should be regarded as adverse events. Abnormal results of diagnostic procedures are considered to be adverse events only if the abnormality:

- results in study withdrawal
- is associated with a serious adverse event
- is associated with clinical signs or symptoms
- leads to additional treatment or to further diagnostic tests is considered by the investigator to be of clinical significance

Adverse Event Reporting Period

The study period during which adverse events must be reported is defined as the period from the initiation of the first study treatment to the last administration of study treatment.

Post-study Adverse Event.

All unresolved adverse events should be followed by the clinical investigator until the events are resolved, the participant is lost to follow-up, or the adverse event is otherwise explained. At the last scheduled visit, the investigator should instruct each participant to report any subsequent event(s) that the participant, or the participant's personal physician, believes might reasonably be related to participation in this study.

Abnormal Laboratory Values.

A clinical laboratory abnormality should be documented as an adverse event if the abnormality is grade 1 or more and a change from baseline.

Recording of Adverse Events.

At each contact with the participant, the appropriately delegated and credentialed study team member must seek information on adverse events by specific questioning and, as appropriate, by examination. Information on all adverse events should be recorded immediately in the source document, and also in the appropriate adverse event module of the case report form (CRF). All clearly related signs, symptoms, and

abnormal diagnostic procedures results should be recorded in the source document, though should be grouped under one diagnosis.

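### Sub-Study 3 adverse-event rate ratio: the AE window ends at the last dose in some sections and runs to 2 months in others, and no exposure term is given, so the arm that stops drug earlier can look safer

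*Protocol*

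**What the plan says.** Under Protocol section 11.0 (Adverse Event Reporting Period), the study period in which AEs must be reported is "defined as the period from the initiation of the first study treatment to the last administration of study treatment"; the SAP repeats it under the same heading as running "from the initiation of the first study treatment to the last administration of study treatment". Protocol 11.1 and the SAP's section on recording AEs then require every AE in the study period to be recorded.

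Other current text reaches further:

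- The opening of Protocol 11.0 makes the sponsor-investigator responsible for seeing that AEs "that are observed or reported during the study are collected".
- Protocol 10.1: "All participants will be evaluable for toxicity from the time of their first treatment with HCQ or placebo". It names no end; section 10.3 supplies one by closing participation at 2 months.
- Protocol Table 6 has the row "AE check by telephone", weekly and again at 2 months, with no condition that drug is still being taken.
- Protocol 10.3 lets people who choose to stop drug stay in the other procedures until 2 months.
- Protocol 8.4.2: an HCQ participant taken off drug for an asymptomatic positive swab at one month is referred for "standard of care management of health care worker infection. Weekly phone calls will continue".
- The SAP's secondary objective takes treatment-related AEs from weekly calls to all subjects.

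For the analysis, Protocol 12.2 (printed inside section 13) says: "Adverse event rates will be summarized as a count by subject, and mean count by group, and we will estimate a rate-ratio for treatment". It also says: "We may conduct exploratory analyses using regression methods appropriate for each type of measure". The SAP safety set is everyone randomised who took a dose. Neither document states a counting window, a person-time denominator or an offset for this ratio.

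**The concern.** A non-serious AE reported on a scheduled call after the last dose is elicited under one set of passages and falls outside the mandatory window under another. Nothing says whether it enters the ratio. Under the last-dose rule, a participant who stops at week 2 contributes two weeks of counting but still a full unit to the per-subject denominator. This gives a lower count rather than a missing value, so the SAP's rule of using only observed values does not help.

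Unequal stopping is foreseeable. Protocol 10.3 ends treatment for a toxicity delay or by choice. Infection is also handled differently by arm: a placebo participant may cross over to HCQ, while an HCQ participant stops. Whether crossover HCQ extends the period of study treatment is not stated. The protocol itself notes (4.1.1) that HCQ has a half-life of many days, so related events after the last dose are plausible.

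Treatment-related AEs are the only Sub-Study 3 secondary objective listed in the protocol, in healthy workers taking a preventive drug. As written, a reader could not tell whether the reported ratio is on-treatment or over 8 weeks.

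**Working it through.** **Inputs.** From the documents: 8 weeks (56 days) of treatment, mean count per subject, no exposure term, and design infection rates of 1% on HCQ and 10% on placebo. The documents give no AE rate, stopping rate or AE ratio, so there is no planned figure to reproduce. Stopping fractions *f*, stopping days *d* and the on-drug rate ratio *RR* are assumed.

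**Formulas** (constant rates). Mean on-drug time per arm is E = (1 − f) × 56 + f × d.

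- Counting to last dose, no offset: RR × E_HCQ / E_placebo.
- Counting all 8 weeks, with the background rate from the day of stopping: (RR × E_HCQ + 56 − E_HCQ) / 56.

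Example: 20% of HCQ stop at day 14 and no placebo participant stops. E_HCQ = 0.8 × 56 + 0.2 × 14 = 47.6, and 47.6 / 56 = 0.85. With RR = 2 the last-dose ratio is 1.70, and the 8-week ratio is (95.2 + 8.4) / 56 = 1.85.

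| Stopping, HCQ / placebo | E_HCQ / E_placebo | Last dose, RR 1.0 | Last dose, RR 2.0 | 8 weeks, RR 2.0 |
|---|---|---|---|---|
| 10% / 0, day 14 | 51.8 / 56 | 0.925 | 1.85 | 1.925 |
| 20% / 0, day 14 | 47.6 / 56 | 0.85 | 1.70 | 1.85 |
| 30% / 0, day 14 | 43.4 / 56 | 0.775 | 1.55 | 1.775 |
| 20% / 0, day 28 | 50.4 / 56 | 0.90 | 1.80 | 1.90 |
| 10% / 20%, day 14 | 51.8 / 47.6 | 1.09 | 2.18 | 1.925 |
| 20% / 20%, day 14 | 47.6 / 47.6 | 1.00 | 2.00 | 1.85 |

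With RR 1.0 the 8-week ratio is 1.00 in every row. A Poisson simulation (100 per arm, assumed 0.1 AE per week, 30% v 10% stopping at week 2, RR 1.0) gives a median of 0.83 without an exposure term and 1.00 with one. The formula gives 6.2 / 7.4 = 0.84.

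**Infection alone**, at 1% v 10% with no drug effect on AEs:

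- If infection ends the window at day d: day 14, 55.58 / 51.8 = 1.073; day 28, 55.72 / 53.2 = 1.047; day 42, 55.86 / 54.6 = 1.023.
- If every infected placebo participant takes 14 days of crossover HCQ and that counts as study treatment: 55.58 / 53.2 = 1.045; 55.72 / 54.6 = 1.02; 55.86 / 56 = 0.998.

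**If excess AEs cluster early.** Suppose HCQ has 56 background plus 56 excess events, the excess all in days 1 to 14, against 56 on placebo (8-week ratio 2.00). With 20% of HCQ stopping at day 14, the count is 0.8 × 112 + 0.2 × 70 = 103.6. Counting to last dose without an offset gives 103.6 / 56 = 1.85. An on-treatment offset gives 103.6 / 47.6 = 2.18. The fixed 8-week window gives 2.00. An offset on drug time alone is therefore not a complete repair.

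**The case against.** The best answer is that the plan already implies an 8-week count. The SAP objective names weekly calls to all subjects, Table 6 runs to 2 months, section 10.3 closes participation at 2 months, and the safety set is everyone dosed. On that view section 11.0 sets only a minimum reporting duty. This is a fair reading, and under it the last-dose distortion does not arise. But no passage states it, and the SAP repeats the last-dose period and ties recording to it. The term rate ratio might hint at person-time, but mean count by group points to a per-subject denominator.

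Several limits on the point stand. The gap between the last-dose and 8-week ratios is not all error, because they answer different questions and the 8-week ratio is itself diluted by stopping (1.85 against 2.00 at equal 20% stopping). The objective concerns treatment-related AEs, whereas the illustrations include background events. No hypothesis test or stopping threshold rests on this ratio.

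A reader might infer that more stopping on HCQ always pulls the ratio toward 1. That holds only when the true ratio exceeds 1 and the shift does not carry it past 1; with no drug effect, 0.85 is a move away from 1. A reader might also infer that any infected HCQ participant leaves AE contact. The off-study clause in 10.3 covers symptomatic PCR-positive participants, while 8.4.2 keeps the calls going for those who are asymptomatic at one month.

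**Conclusion.** The point holds as a low-impact inconsistency in a secondary safety summary. Current passages disagree on whether non-serious AEs after the last dose are recorded, and the analysis has no exposure term that would make the choice harmless. Under the last-dose rule the ratio is multiplied by E_HCQ / E_placebo, so the arm that stops earlier looks safer; balanced stopping leaves the on-drug ratio unbiased.

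The size is unknown. The figures rest on assumed stopping fractions, constant rates and, for the 8-week ratio, an immediate return to background; given the long half-life, dilution could be smaller. Infection alone does little: about 1.02 to 1.07 if it ends the window, or about 1.00 to 1.045 if crossover HCQ counts. Those figures use the design alternative, which is not a forecast.

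The documents do not support reading this as a threat to the trial's main conclusion. Serious AEs have their own collection rule from consent (Protocol 11.1.1), and the primary test and the QTc endpoint do not use this window.

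**What to change.** 1. Amend the reporting-period text in Protocol 11.0 and the SAP so that non-serious AEs are recorded and counted from first dose to the 8-week contact for every dosed participant still in contact, in both arms, whether or not drug was stopped, using the weekly calls already planned.
2. Compute the Protocol 12.2 rate ratio by randomised arm over that window, for treatment-related AEs (the stated objective) and for all AEs, with log follow-up time as offset.
3. Report an on-treatment person-time ratio beside it. The 8-week ratio is diluted by stopping and the on-treatment ratio is distorted if AEs cluster early, so neither is enough alone.
4. List AEs after crossover to HCQ separately, since the as-randomised ratio counts that time under placebo. With RR 2.0, infection at day 28 in 1% v 10% and 14 days of crossover HCQ, it is (0.99 × 112 + 0.01 × 84) / (0.9 × 56 + 0.1 × 70) = 111.72 / 57.4 = 1.95.
5. For AE contact only, reconcile the off-study clause in Protocol 10.3 with the continuing calls in 8.4.2 and the SAP's calls to all subjects. Align the symptom-monitoring text in 8.4.2, which has coordinators document likely treatment-related events, with the requirement in Protocol 11.1 and the SAP to record all AEs.

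The cost is wording changes in two documents, one extra analysis and a few more low-grade AEs to record. No new visits or calls are needed.

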11.1.1 Serious Adverse Events

Adverse events are classified as serious or non-serious.

A serious adverse event is any AE that is:

- fatal
- life-threatening
- requires or prolongs hospital stay
- results in persistent or significant disability or incapacity
- a congenital anomaly or birth defect
- Suspected transmission of an infectious agent (eg, pathogenic or nonpathogenic) via the study drug is an

The PATCH Trial
SAE.

- an important medical event

Important medical events are those that may not be immediately life threatening, but are clearly of major clinical significance. They may jeopardize the participant, and may require intervention to prevent one of the other serious outcomes noted above. For example, drug overdose or abuse, a seizure that did not result in in-patient hospitalization, or intensive treatment of bronchospasm in an emergency department would typically be considered serious. Theft, sale, or use of the study product by any person other than the participant will be reported as a medically important event.

ADVERSE EVENT COLLECTION AND REPORTING INFORMATION:

- All Serious Adverse Events (SAEs) that occur following the participant's written consent to participate in the study must be reported, whether related or not related to study drug. If applicable, SAEs must be collected that relate to any later protocol-specified procedure.
- Following the participant's written consent to participate in the study, all SAEs, whether related or not related to study drug, are collected, including those thought to be associated with protocol-specified procedures. The investigator-sponsor should report any SAE occurring after these aforementioned time periods, which is believed to be related to study drug or protocol-specified procedure.
- An SAE report should be completed for any event where doubt exists regarding its seriousness;
- If the investigator believes that an SAE is not related to study drug, but is potentially related to the conditions of the study (such as withdrawal of previous therapy or a complication of a study procedure), the relationship should be specified in the narrative section of the SAE ReportForm.

All SAEs should be followed to resolution or stabilization.

Adverse events can be spontaneously reported or elicited during open-ended questioning, examination, or evaluation of a participant. (In order to prevent reporting bias, participants should not be questioned regarding the specific occurrence of one or more AEs.)

All adverse events that do not meet any of the criteria for serious should be regarded as non-serious adverse events. Non-serious adverse events are documented and assessed as adverse events noted above.

Hospitalization, Prolonged Hospitalization or Surgery.

Any adverse event that results in hospitalization or prolonged hospitalization should be documented and reported as a serious adverse event unless specifically instructed otherwise in this protocol. Any condition responsible for surgery should be documented as an adverse event if the condition meets the criteria for an adverse event.

Neither the condition, hospitalization, prolonged hospitalization, nor surgery are reported as an adverse event in the following circumstances:

- Hospitalization or prolonged hospitalization for diagnostic or elective surgical procedures for a preexisting condition. Surgery should not be reported as an outcome of an adverse event if the purpose of the surgery was elective or diagnostic and the outcome was uneventful.
- Hospitalization or prolonged hospitalization required to allow efficacy measurement for the study.
- Hospitalization or prolonged hospitalization for therapy of the target disease of the study, unless it is a worsening or increase in frequency of hospital admissions as judged by the clinical investigator.

Property of University of Pennsylvania
Confidential

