All adverse events occurring during the study period must be recorded. Adverse events will be measured and graded in accordance with the CTCAE v 5.0. The clinical course of each event should be followed until resolution, stabilization, or until it has been determined that the study treatment or participation is not the cause. Serious adverse events that are still ongoing at the end of the study period must be followed up to determine the final outcome. Any serious adverse event that occurs after the study period and is considered to be at least possibly related to the study treatment or study participation should be recorded and reported immediately.

Serious Adverse Events

Adverse events are classified as serious or non-serious.

A serious adverse event is any AE that is:

- fatal
- life-threatening
- requires or prolongs hospital stay
- results in persistent or significant disability or incapacity
- a congenital anomaly or birth defect
- Suspected transmission of an infectious agent (eg, pathogenic or nonpathogenic) via the study drug is an SAE.
- an important medical event

Important medical events are those that may not be immediately life threatening, but are clearly of major clinical significance. They may jeopardize the participant, and may require intervention to prevent one of the other serious outcomes noted above. For example, drug overdose or abuse, a seizure that did not result in in-patient hospitalization, or intensive treatment of bronchospasm in an emergency department would typically be considered serious. Theft, sale, or use of the study product by any person other than the participant will be reported as a medically important event.

DSMB Description

The Data and Safety Monitoring Board (DSMB) for the Prevention And Treatment of COVID-19 with Hydroxychloroquine (PATCH) trial has been selected by the Sponsor- Principal Investigator [name] and acts in an advisory capacity to [name] for the PATCH trial to monitor participant safety, data quality and evaluate the progress of the study.

The DSMB will consist of 5 members:

[name], expertise in Emergency medicine, Chair of DSMB

[name], expertise in infectious disease

[name]: expertise in biostatistics,

[name]: expertise in clinical trials and therapeutics

[name]: expertise in clinical trials and cardiology

This DSMB will be independent of the Sponsor, regulatory agencies, IRBs/ECs, and investigators.

DSMB Membership

Requirements for Membership

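### In SS3, Protocol 11.1.1 leaves reporting of non-fatal COVID-19 admissions to investigator judgement, and no SS3 endpoint records them

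*Protocol*

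**What the plan says.** Protocol 11.1.1 starts from a general rule. An adverse event that leads to hospitalization "should be documented and reported as a serious adverse event unless specifically instructed otherwise in this protocol". Exceptions follow, introduced by: "Neither the condition, hospitalization, prolonged hospitalization, nor surgery are reported as an adverse event in the following circumstances". One of them is "Hospitalization or prolonged hospitalization for therapy of the target disease of the study, unless it is a worsening"; the limit reads in full "unless it is a worsening or increase in frequency of hospital admissions as judged by the clinical investigator". The text has no separate rule for SS3 and does not say what the target disease means for people who enrol to prevent it.

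Two other rules in 11.1.1 point towards reporting. SAEs after consent "must be reported, whether related or not related to study drug", and "An SAE report should be completed for any event where doubt exists regarding its seriousness".

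The SAP is written for SS3 alone. Its section on adverse event reporting opens: "The timely reporting of adverse events (including hospitalizations and deaths) is required by the Food and Drug Administration". Its definition of a serious adverse event includes any adverse event that "requires or prolongs hospital stay". It repeats none of the exceptions in Protocol 11.1.1.

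The SS3 endpoints are PCR-defined infection (primary) and treatment-related adverse events (secondary). The SAP's amendment table adds QTc change, and its analysis-set table lists antibody prevalence. Rate of hospitalization is a secondary objective of SS1 only (Protocol 1.2).

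**The concern.** In a trial of hospitalised patients, an admission for the disease under study is background, and an exemption of this kind is understandable. The same bullet appears in the original protocol, which still included a hospitalised sub-study (SS2). SS2 has closed, and the bullet now governs a home-quarantine sub-study and a prevention sub-study. In SS3 a COVID-19 admission is among the most serious outcomes a participant can have.

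What is at stake is the comparison of non-fatal severity between arms. The primary endpoint counts the infection, not whether it led to hospital. If the admission is also kept out of adverse event reporting, neither the DSMB report nor the final safety table need show it. The decision is also exposed to knowledge of treatment: under Protocol 5.0, 7.5 and 8.4.2, SS3 participants who turn PCR-positive on study are generally unblinded.

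**Working it through.** The point rests on how the passages fit together; the plan has no figure of its own to reproduce.

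1. **Does the exemption reach a COVID-19 admission in SS3?** The trial's title names COVID-19 as the disease to be prevented and treated, and the bullet is not limited to any sub-study. On its face it does.

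2. **Do the other rules in 11.1.1 override it?** The SAE collection rule and the rule on doubtful seriousness concern events that already count as adverse events. The exemption acts one step earlier, by saying that the condition and the admission are not reported as adverse events at all. The two rules therefore do not clearly restore what the exemption removes.

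3. **Does the exemption's own limit restore it?** Often, yes. Protocol 10.1 requires a negative PCR for the SS3 primary outcome, so an admission for COVID-19 in such a participant is naturally read as a worsening. But the text leaves that reading to each investigator.

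4. **Does an SS3 endpoint capture it anyway?** Infection, QTc change and antibody prevalence do not. The secondary endpoint covers treatment-related events only, so even a reported admission judged unrelated to study drug falls outside it.

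5. **Would both arms be observed alike?** The adverse event period ends at the last dose (Protocol 11.0; SAP, Adverse Event Reporting Period). Under Protocol 10.3, a symptomatic, test-positive participant on HCQ goes off study, while one on placebo may cross over and stay on for 14 days or until release from quarantine. If crossover drug counts as study treatment, the placebo participant's reporting period is longer. SAEs after the study period are to be recorded when considered at least possibly related. A later HCQ-arm admission judged unrelated could therefore be missed where a placebo-arm one is seen.

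6. **How many admissions?** The infection rates are those of Protocol 13.1: 10% on placebo and 1% on HCQ, with 100 per arm. The admission rate a is assumed to be 5–20%.

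| Quantity | Formula | a = 5% | a = 20% |
|---|---|---|---|
| Placebo infections | 100 × 0.10 = 10 | | |
| HCQ infections | 100 × 0.01 = 1 | | |
| Admissions, placebo | 10 × a | 0.5 | 2.0 |
| Admissions, HCQ | 1 × a | 0.05 | 0.2 |
| Admissions, both arms | 11 × a | 0.55 | 2.2 |

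The last row is an upper bound on what the exemption could remove under these assumptions, because admissions judged a worsening would be reported.

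**The case against.** The strongest reply is that the limit on the exemption already covers nearly every case. Someone who enrols PCR-negative and is later admitted with COVID-19 has plainly got worse, and the rule on doubtful seriousness pushes the same way. Much of this stands. It reduces the problem to one of discretion, but does not remove it, because nothing in the text makes that reading compulsory.

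Several stronger conclusions might be inferred, and the documents do not support them.

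- *SS1 admissions are lost too.* They are not. Rate of hospitalization is an SS1 secondary objective, with rates by group and an odds ratio planned in Protocol 12.2. At most they would be absent from SAE tables.
- *The DSMB could not see harm from more COVID-19 on HCQ.* An excess of infections is the primary endpoint, which is compared by arm and goes to the DSMB at both interim analyses. Deaths in the reporting period are reported whatever the attribution (Protocol 11.2.4). Only non-fatal severity is at issue.
- *The SAP contradicts the protocol.* The SAP reproduces much of the protocol's adverse event text and stops before the exceptions. That is an omission, not a rejection, and its sentence naming hospitalizations is introductory. Still, a reader of the SAP alone would expect every such admission to be reported.
- *Reporting will be biased by arm.* The documents show how it could differ, not that it would. With an expected 0.05 to 0.2 admissions on HCQ, no formal comparison between arms is possible.

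**Conclusion.** The point holds for SS3 in a limited form. A stated protocol rule allows a non-fatal COVID-19 admission to go unreported as an adverse event. The safeguard is an investigator's judgement, often made with the arm known, and no SS3 endpoint records the admission. The SS3 SAP gives no sign that such an exemption exists.

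The size is small: about 0.6 to 2.2 admissions among roughly 11 expected infections. This rests on the design infection rates being right and on the assumed 5–20% admission rate, and it would scale with either. The primary analysis is unaffected. The reason to act is that the participants are healthcare workers taking a drug for prevention, so each admission matters individually, and the correction is cheap.

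**What to change.** Three changes, all to safety reporting and follow-up; none alters treatment.

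- In Protocol 11.1.1, state that the target-disease exception does not apply to SS3, and say the same in the SAP's adverse event section.
- Record every COVID-19 hospitalization in SS3 as an SAE in both arms, from consent to the planned two-month end of follow-up. Include participants who are off study drug, or off study after a positive test. This means reconciling Protocol 10.3 and the reporting period in Protocol 11.0 and the SAP. Removing the exception alone would not secure equal capture by arm.
- Tabulate these admissions by randomised arm in the DSMB reports and the final SS3 safety table. The SAP does not currently call for this.

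The cost is a few more SAE forms, plus some follow-up contact with participants who would otherwise have left the study. SS1 needs no change on this point.
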